9.3.2 Exclusion Criteria

Subjects who meet any of the following criteria will be excluded from this study:

1. Any neurological condition that may be contributing to cognitive impairment above and beyond that caused by the subject's AD pathology, including any co-morbidities detected by neurological examination or MRI
2. Modified Hachinski Ischemic Scale >4
3. History of transient ischemic attacks or stroke within 12 months of Screening
4. A history of epilepsy. Subjects with a history of seizures (not including a history of simple febrile seizures in childhood) within 10 years of Screening. Subjects with disturbance likely to be due to seizures within 5 years of Screening.
5. Significant pathological findings on the brain MRI at Screening, including but not limited to: more than 4 microhemorrhages (defined as 10 mm or less at the greatest diameter), any microhemorrhage which is symptomatic, a single macrohemorrhage greater than 10 mm at greatest diameter, an area of superficial siderosis, evidence of vasogenic edema, greater than 3 lacunar infarcts or a single infarct >2 cubic centimeters involving a major vascular territory, evidence of severe microangiopathy, evidence of cerebral contusion, encephalomalacia, aneurysms, vascular malformations, infective lesions or space-occupying lesions (however, lesions diagnosed as arachnoid cysts and <1cm in diameter at their greatest diameter need not be exclusionary) or brain tumors (eg, meningioma). (revised per Amendment 01)
6. Any psychiatric diagnosis or symptoms, (eg, hallucinations, major depression, or delusions) that could, in the opinion of the investigator, confound the MCI/Prodromal or mild to moderate AD diagnosis or could interfere with study assessments or procedures (revised per Amendments 01 and 02)
7. A score of ≥ 8 on the 15-item Geriatric Depression Scale (GDS) at Screening
8. Abnormally low serum vitamin B12 (<LLN) levels for the testing laboratory (if subject is taking vitamin B12 injections, level should be at or above the LLN for the testing laboratory) at Screening
9. Thyroid stimulating hormone above the normal range. Other tests of thyroid function with results outside the normal range should only be exclusionary if they are considered clinically significant by the investigator. This applies to all subjects regardless of whether or not they are taking thyroid supplements.

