9.3.3 Removal of Subjects from Therapy or Assessment

The investigator may discontinue study drug or withdraw the subject from the study at any time for safety or administrative reasons. The subject may decide to stop study drug or withdraw from the study at any time for any reason.

Subjects who discontinue taking study drug prematurely for any reason will undergo an ED Visit within 7 days of their last dose of study drug (see [Section 9.1.2.2](#)). Follow-Up Visits will also be scheduled 2, 4, 8, and 12 weeks after the last dose of study drug in the Core Study (see [Section 9.1.2.3](#)), and 4 and 12 weeks after the last dose of study drug in the OLE Phase (see [Appendix 6](#)). (revised per Amendments 04, 05 and 07)

The primary reason for discontinuation and all other reason(s) contributing to the subject's discontinuation from study drug(s) should be collected on the Subject Disposition eCRF page. In addition, the date of last dose of study drug(s) will be recorded on the Study Drug Dosing eCRF page. If a subject discontinues study drug and withdraws from the study at the same time, the ED Visit will be followed (see [Section 9.5.5](#)).

Safety-related criteria for discontinuation of study drug during the Core Study include the following: (revised per Amendments 07)

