- f. Development of any of the following features on MRI: vasogenic edema, macrohemorrhage, an area of superficial siderosis, or a symptomatic microhemorrhage. If discontinued from study drug, subjects will undergo an ED Visit within 7 days after discontinuation and will attend the Follow-Up Visits 2, 4, 8, and 12 weeks after the last dose of study drug. They will also undertake an Unscheduled Visit (with MRI) at approximately 4 weeks after the visit at which such MRI features were first identified. An MRI will also be performed at approximately the time of the final Follow-Up Visit (Visit 20). Additional visits for safety may be arranged if clinically indicated in the opinion of the investigator, including after 12 weeks after the last dose of study drug. At any time during the treatment period, subjects who have asymptomatic, treatment-emergent microhemorrhages as detected by MRI, but none of the features which merit discontinuation of treatment (ie, vasogenic edema, macrohemorrhage, an area of superficial siderosis, or a symptomatic treatment-emergent microhemorrhage) may continue with treatment. These subjects will have safety assessments (including MRI) at approximately 4 weeks after the visit at which such MRI features were found. They will also continue with the scheduled MRI scans. Additional unscheduled MRI scans may be arranged on an individual subject basis in discussion with the study medical monitor. (revised per Amendment 04)
- g. A postdose ECG with an average QTcF interval >500 msec from triplicate ECGs
- h. A postdose ECG with a QTcF interval increase from baseline >60 msec and a QTcF interval >450 msec as demonstrated from triplicate ECGs
- i. Any seizure (motor or non-motor)
- j. Pregnancy

Safety-related criteria for discontinuation of study drug during the OLE Phase are provided in [Appendix 6](#). (revised per Amendment 07)

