The following AEs will require the collection of information sufficient to provide a detailed description of the event, treatment and outcome to the Medical Monitor for the study: any treatment-emergent significant laboratory abnormality; any seizures, herpes zoster infection, severe infection; any moderate to severe drug rash or any rash lasting more than 72 hours (regardless of severity); amyloid-related imaging abnormalities (vasogenic edema, macrohemorrhage, an area of superficial siderosis, or a new microhemorrhage); a “yes” answer to Type 4 or 5 suicidal ideation, or a “yes” response to any suicidal behavior on the C-SSRS.

All AEs must be followed through the final Follow-Up visit (Visit 20 for subjects who do not enter the OLE Phase or Visit 34 for subjects who participate in the OLE Phase), or until resolution, whichever comes first. (revised per Amendment 07) All SAEs must be followed to resolution or, if resolution is unlikely, to stabilization. (revised per Amendment 04)

Every effort must be made by the investigator to categorize each AE according to its severity and its relationship to the study treatment.

Assessing Severity of Adverse Events

AEs will be graded on a 3-point scale (mild, moderate, severe) and reported in the detail indicated on the eCRF. The definitions are as follows:

Mild Discomfort noticed, but no disruption of normal daily activity

Moderate Discomfort sufficient to reduce or affect normal daily activity

Severe Incapacitating, with inability to work or to perform normal daily activity

The criteria for assessing severity are different than those used for seriousness (see [Section 9.5.1.5.2](#) for the definition of an SAE).

Assessing Relationship to Study Treatment

Items to be considered when assessing the relationship of an AE to the study treatment are:

- Temporal relationship of the onset of the event to the initiation of the study treatment
- The course of the event, especially the effect of discontinuation of study treatment or reintroduction of study treatment, as applicable
- Whether the event is known to be associated with the study treatment or with other similar treatments
- The presence of risk factors in the study subject known to increase the occurrence of the event
- The presence of nonstudy, treatment-related factors that are known to be associated with the occurrence of the event

Classification of Causality

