Eligible subjects who choose to participate in the OLE Phase may enter the OLE Phase immediately following the completion of Visit 20 (ie, Visit 21 procedures may be completed on the same day as Visit 20). Subjects who are eligible to participate in the OLE Phase but who do not transition to the OLE Phase on the day of Visit 20 may enter the OLE Phase any time within 4 weeks of Visit 20. The Medical Monitor must be contacted if Visit 21 is to occur more than 4 weeks after Visit 20. For all subjects, assessments performed at V20 may serve as baseline values for the OLE Phase (ie, results of assessments conducted at Visit 21) with exceptions of laboratory assessments and vital signs, which must be repeated if Visit 21 occurs more than 10 days from Visit 20.

During the OLE Phase, subjects will receive open-label elenbecestat (E2609) 50 mg per day for up to 24 months. Subjects with pending INR and serum pregnancy test results (females subjects of child bearing potential only) but who are otherwise qualified may begin OLE dosing at Visit 21; however, these subjects must discontinue study drug treatment immediately if either test result meet the exclusion criteria.

Safety assessments will be performed as described in [Table 14](#). Subjects may discontinue from study drug for any reason. Subjects who complete 24 months of OLE treatment or who discontinue the study drug must comply with the Early Discontinuation Visit (within 7 days after the last dose of study drug) and the Follow-Up Visits (weeks 4 and 12 after the last dose of study drug).

The study will end when the last visit for the last subject has completed the OLE Phase.

Removal of Subjects from Therapy or Assessment

The investigator may discontinue study drug or withdraw the subject from the study at any time for safety or administrative reasons. The subject may decide to stop study drug or withdraw from the study at any time for any reason. Subjects who discontinue study drug prematurely for any reason will undergo an ED Visit within 7 days of their last dose of study drug. Subjects who discontinue from treatment during the OLE will have 2 posttreatment Follow-Up visits at 4 and 12 weeks after the last dose of study drug.

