The primary reason for discontinuation and all other reason(s) contributing to the subject's discontinuation from study drug should be collected on the ED from study drug electronic case report form (eCRF) page (see Protocol [Section 9.5.5](#)). In addition, the date of last dose of study drug will be recorded on the Study Drug Dosing eCRF page.

Safety-related criteria for discontinuation of study drug include the following:

1. Absolute lymphocyte count will be monitored during the study. Should a subject develop lymphocytopenia (less than $800/\text{mm}^3$ or LLN, whichever is higher), a confirmation test should occur as soon as possible but no later than within 5 days with a repeat test of absolute lymphocytes. If confirmed, study drug administration should be interrupted for a minimum period of 2 weeks. Restart of study drug may take place only when absolute lymphocyte count returns to greater than LLN. Absolute lymphocyte count will be measured 4 weeks after restart of study drug. Subsequent measurements of absolute lymphocyte counts will follow the schedule of assessments and any results showing a Grade 2 or greater lymphocytopenia (less than $800/\text{mm}^3$) should be handled as above. If a 2nd occurrence of Grade 2 or greater lymphocytopenia (less than $800/\text{mm}^3$), that is confirmed on repeat testing, occurs within 6 months, then the subject should be discontinued permanently from the study drug.
2. A subject with any skin rash of moderate to severe intensity, or any rash lasting more than 72 hours regardless of severity (with the exception of oral or genital herpes as described in the next paragraph), will be discontinued from study drug and a dermatologic consult will be requested regardless of whether the rash is considered drug-related or due to other causes. For cases where the investigator suspects a drug rash, regardless of severity, the subject will be discontinued from study drug, a dermatologic consult will be requested, and a skin biopsy will be performed to confirm the diagnosis. The skin rash will be treated as per standard care and will be followed up until resolution regardless of etiology or severity.
3. Subjects who develop moderate to severe oral or genital herpes should be discontinued from study drug. Subjects who develop a mild case of oral or genital herpes may remain on study drug even if the event lasts more than 72 hours.

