4. Development of any of the following features on MRI: vasogenic edema, macrohemorrhage, an area of superficial siderosis, or a symptomatic microhemorrhage. If discontinued from study drug, subjects will undergo an ED Visit within 7 days after discontinuation. They will also undertake an Unscheduled Visit (with MRI) at approximately 4 weeks after the visit at which such MRI features were first identified. Additional visits for safety may be arranged if clinically indicated in the opinion of the investigator, including after 12 weeks after the last dose of study drug. At any time during the treatment period, subjects who have asymptomatic, treatment-emergent microhemorrhages as detected by MRI, but none of the features which merit

discontinuation of treatment (ie, vasogenic edema, macrohemorrhage, an area of superficial siderosis, or a symptomatic treatment-emergent microhemorrhage) may continue with treatment. These subjects will have safety assessments (including MRI) at approximately 4 weeks after the visit at which such MRI features were found. They will also continue with the scheduled MRI scans. Additional unscheduled MRI scans may be arranged on an individual subject basis in discussion with the study medical monitor.

5. Pregnancy
6. A postdose ECG with an average QTcF interval >500 msec from triplicate ECGs.
7. A postdose ECG with a QTcF interval increase from baseline >60 msec and a QTcF interval >450 msec as demonstrated from triplicate ECGs.

Treatments

During the OLE Phase, all subjects will receive open-label elenbecestat (E2609) 50 mg once a day. Each subject will take 1 tablet orally QD, with food. Please refer to [Table 14](#) for specific information on drug administration on days when PD sampling is to be performed.

EXTENSION PHASE ASSESSMENTS

Safety assessments will continue to be monitored according to the Schedule of Assessments and all adverse events (AEs) and serious adverse events (SAEs) recorded. All safety assessments (eg, physical examinations, neurological examinations, vital signs, hematology, blood chemistry, serum and urine pregnancy test for females of child bearing potential, safety MRI and vMRI) will be performed as described in [Table 14](#). The number of blood samples and the total volume of blood that will be collected throughout OLE Phase is summarized in [Table 13](#).

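### Any seizure stops study drug in the Core Study, but the Appendix 6 stopping list for the open-label extension omits it

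*Protocol*

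**What the plan says.** Section 9.3.3 opens its list a to j with "Safety-related criteria for discontinuation of study drug during the Core Study include the following". Criterion i of that list reads "Any seizure (motor or non-motor"). The section then closes with "Safety-related criteria for discontinuation of study drug during the OLE Phase are provided in" Appendix 6.

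Appendix 6, under Removal of Subjects from Therapy or Assessment, has its own lead-in, "Safety-related criteria for discontinuation of study drug include the following", followed by seven items: lymphocytopenia, rash, oral or genital herpes, MRI features, pregnancy and two QTcF rules. The last is "A postdose ECG with a QTcF interval increase from baseline >60 msec and a QTcF interval >450 msec as demonstrated from triplicate ECGs". For anything not listed, the appendix gives a general permission: "The investigator may discontinue study drug or withdraw the subject from the study at any time for safety or administrative reasons".

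Elsewhere the protocol treats seizure as important:

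- Section 9.3.2, criterion 4, excludes epilepsy and "Subjects with a history of seizures (not including a history of simple febrile seizures in childhood) within 10 years of Screening".
- Section 9.5.1.5.1 requires a detailed account to the Medical Monitor for events that include "any seizures, herpes zoster infection, severe infection".
- Section 9.5.1.5.2 classes new-onset seizures as always serious, and section 9.5.4.1 requires serious events to be reported within 24 hours.

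**The concern.** The same event on the same drug leads to different actions in the two phases. A subject with a seizure during Core treatment must stop, may not restart (section 9.5.5) and cannot enter the OLE (Appendix 6, exclusion 1). If the seizure comes during the OLE, no rule requires stopping.

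The OLE gives everyone 50 mg, the highest study dose, for up to 24 months. For some subjects it is their first exposure to that dose: former placebo subjects, and any 5 or 15 mg subjects who stayed on their randomized dose because they had completed Visit 17 before Amendment 06 took effect (section 9.1). For them no mandatory seizure stop ever applies while they take 50 mg.

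**Working it through.** The plan gives no figure to reproduce; the check is a comparison of the two lists.

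| Core Study (9.3.3) | OLE (Appendix 6) |
|---|---|
| a. CD4/CD8/CD19 below the stopping threshold | 1. Absolute lymphocyte count (rewritten) |
| b. Counts between LLN and threshold | none of its own |
| c. Infection, shingles, ocular herpes | none |
| d. Rash | 2 |
| e. Oral or genital herpes | 3 |
| f. MRI features | 4 |
| g. Mean QTcF >500 msec | 6 |
| h. QTcF rise >60 msec with QTcF >450 msec | 7 |
| i. Any seizure | **none** |
| j. Pregnancy | 5 |

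Seven of the ten Core criteria have an OLE counterpart (eight if b is regarded as absorbed into item 1). Within the run d to j, six of seven carry over and only i is missing, although h and j on either side of it were kept.

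Next, does any other provision require a stop after an OLE seizure?

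- Sections 9.5.1.5.1, 9.5.1.5.2 and 9.5.4.1 are reporting duties.
- Section 9.4.1 asks for a discussion with the medical monitor about temporary suspension for a concurrent illness, and allows dosing to resume.
- Section 9.5.1.5.9 leaves the work-up of new neurological signs to case-by-case discussion with the medical monitor.
- Appendix 6 item 4 stops drug only if a listed MRI feature is found; a seizure without one is not covered.
- The general clause in Appendix 6 permits stopping but does not require it.

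None makes stopping mandatory.

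Upper bounds on the number of subjects affected, from section 9.1 (about 60 ± 20% randomized, 1:1:1:1; OLE up to 24 months):

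- Randomized: 60 × 0.8 = 48 to 60 × 1.2 = 72.
- OLE exposure: 48 × 2 years = 96 to 72 × 2 years = 144 subject-years.
- Former placebo: 48/4 = 12 to 72/4 = 18.
- 5 and 15 mg arms together: 2 × 12 = 24 to 2 × 18 = 36. The share not re-assigned is not given; assume anything from 0 to 100%.
- First 50 mg exposure in the OLE, upper bound: 12 + 0 = 12 to 12 + 24 = 36 if 48 were randomized; 18 + 0 = 18 to 18 + 36 = 54 if 72 were.

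All are ceilings, since they assume every subject completes the Core Study, enters the OLE and stays two years.

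**The case against.** The protocol scopes the two lists separately, so criterion i never claimed to govern the OLE. The summary of stopping domains in section 9.2.5 names seizure for neither phase, so no stated commitment is broken. The OLE is also a lighter regime by design: single ECGs in place of triplicate, no central dermatology review, absolute lymphocytes in place of subset thresholds. A shorter stopping list could be part of that.

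The list is open-ended, so an investigator can stop drug after a seizure, and a new-onset seizure would reach the sponsor within 24 hours. Subjects who stopped for a seizure in the Core Study are already screened out. The Amendment 07 change log is not among the parts shown, so a deliberate decision cannot be excluded. The exposure figures are sample-size ceilings, and no seizure rate is available.

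Most of this stands and limits how strongly the point can be put. It does not close the gap. The Core list is introduced by the same open-ended wording, yet the sponsor still named seizure there. Lighter monitoring explains fewer assessments, but a seizure stop needs none. Prompt reporting and medical monitor contact make a sensible decision likely, but they do not require the drug to be stopped.

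**Conclusion.** The concern holds. As written, stopping open-label 50 mg after a seizure is discretionary, whereas in the Core Study it is mandatory. The gap covers all OLE subjects, at most 48 to 72 people and 96 to 144 subject-years, including at most 12 to 54 with first exposure to 50 mg in the OLE, depending on the number randomized and the unknown share of 5 and 15 mg subjects not re-assigned.

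The textual difference is certain; whether it was intended is not. The text shown gives no reason for it and reports no seizure signal for the drug. This should be changed as an inexpensive safety improvement that restores the sponsor's own Core rule.

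**What to change.** Add the seizure criterion to the Appendix 6 stopping list as item 8, in the same words as section 9.3.3, criterion i. A sentence explaining the omission would settle whether it was intended but would leave the gap in place.

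The cost is one line of text, with no added visits or assessments. The downside is that a few OLE subjects may stop drug who might otherwise have continued at the investigator's discretion, a consequence the sponsor already accepted in the Core Study.

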9.4 Treatments

9.4.1 Treatments Administered

For the Core Study, the test drug is elenbecestat (E2609) and the control drug is placebo. (revised per Amendments 07) All study drugs are to be administered orally, QD, with food.

Treatments to be administered during the Core Study are 5, 15, and 50 mg elenbecestat (E2609) or placebo prior to the implementation of Amendment 06, and 50 mg elenbecestat (E2609) or placebo after the implementation of Amendment 06 as shown in [Figure 1](#). (revised per Amendments 01, 05, 06, and 07) Study treatment will begin on Day 1 (at the study site) following Randomization and will continue for approximately 78 weeks. Please refer to [Table 7](#) and [Section 9.5.1.4.1](#) for specific information on drug administration on days when PK sampling is to be performed.

Treatments to be administered during the OLE Phase are described in [Appendix 6](#). (revised per Amendment 07)

Study drug doses will remain the same for each individual subject unless the interim PK/PD analysis determines that an entire dose level requires adjustment ([Section 9.4.4](#)). See [Section 9.3.3](#) for safety-related discontinuation criteria of study drug. If a subject develops a concurrent illness during the treatment period, the investigator should discuss with the medical monitor on whether dosing with study drug needs to be temporarily suspended. As a general clinical guideline, dosing with study drug may be resumed after resolution or stabilization of the concurrent illness, after discussion with the medical monitor.

9.4.2 Identity of Investigational Product

Elenbecestat (E2609) tablets of 5-, 10-, and 25-mg dose strengths will be supplied. Placebo tablets of identical appearance will also be available. Each subject will receive 2 tablets, which combined will make up the required doses of elenbecestat (E2609) 5, 15, 50 mg, or placebo. The tablets will be supplied by the Sponsor in labeled blister packs. The product release certificates for elenbecestat (E2609) and placebo will be included in the clinical study report for this protocol.

Subjects will be stratified and randomized, and drug will be dispensed, via an interactive voice and web response system (IxRS) system (see [Section 9.4.3](#)).

The sponsor will provide the study drugs packaged in a double-blind configuration. Each subject's study tablets will consist of either elenbecestat (E2609) or placebo, or both (see [Section 9.4.2.3](#) for labeling details).

